Table 4: Probability of Observing at Least One Unsolicited AE, Solicited Local AE, or Solicited Systemic AE by Assumed True Event Rates	11
Table 5: Expected Precision of GMC Ratio by Assumed Standard Deviation (SD) of Log ₁₀ Antibody Concentration and GMC Ratio with Different Sample Sizes	12
Table 6: Conventions for Presentation	19
Table 7: Conventions for Calculation and Tabulation.....	19
Table 8: Study Visits	20
Table 9: Solicited Reactions Toxicity Grading Scales	21
Table 10: Serum and Hematology Toxicity Grading	22
Table 11: Vital Signs Toxicity Grading.....	23

List of Abbreviations

ABBREVIATION	DEFINITION
Ab	antibody
AE	adverse event
alum	aluminum phosphate
ALT	alanine transaminase
ANCOVA	Analysis of covariance
AST	aspartate aminotransferase
ATC	Anatomical therapeutic chemical
CCfV	Canadian Center for Vaccinology
CI	confidence interval
CONSORT	Consolidated Standards of Reporting Trials
CRF	case report form
CRM ₁₉₇	Cross Reactive Material 197
CRO	contract research organization
DSMB	Data and Safety Monitoring Board
ECLIA	electrochemiluminescence immunoassay
ELISA	enzyme-linked immunosorbent assay
FA	full analysis
GMC	Geometric Mean Concentration
GMFR	Geometric Mean Fold Rise
GMR	Geometric Mean Ratio
GMT	Geometric Mean Titer
HBsAg	Hepatitis B virus surface antigen
HCV	Hepatitis C virus
Hgb	hemoglobin
Hib	Haemophilus influenzae type b
HIV	human immunodeficiency virus
HZ	hydrazide
ID	identification
IgG	immunoglobulin G
IP	investigational product
IPD	invasive pneumococcal disease
IVT PCV-25	25-valent candidate pneumococcal conjugate vaccine manufactured by Inventprise LLC
IWRS	Interactive Web Response System
LLOQ	lower limit of quantification
LSLV	last subject last visit
MedDRA	Medical Dictionary for Regulatory Activities
OPA	opsonophagocytic assay

PCV	pneumococcal conjugate vaccine
PCV-13	13-valent pneumococcal conjugated vaccine (Pneumar 13 [®] ; Pfizer)
PE	physical examination
PEG	polyethylene glycol
PI	Principal Investigator (the term is used throughout to indicate PI or designee)
Plts	platelets
PSRT	Protocol Safety Review Team
PP	per protocol
PT	Preferred Term
RCD	reverse cumulative distribution
SAE	serious adverse event
SD	standard deviation
SOC	System Organ Class
SOP	standard operating procedure
T bili	total bilirubin
TEN	Toxic epidermal necrolysis
TMF	Trial Master File
ULOQ	upper limit of quantification
USA	United States of America
V	Visit
WBC	white blood cell
WHO	World Health Organization
WHO DD	WHO Drug Dictionary
WOCBP	women of childbearing potential

Revision History

Version	Date	Protocol Version	Note
1.0	17-Jan-2024	2.0	
 First approved version
2.0	11-Apr-2024	4.0	
 Revised to include early OPA analyses

1 Introduction

The bacterium *Streptococcus pneumoniae* kills approximately 300,000 children before their fifth birthday annually, mostly in low-resource areas of the world. The most common cause of childhood morbidity and mortality due to the bacterium is pneumonia, which in 2019 was estimated to be the cause of roughly 740,000 under-five deaths worldwide.

Inventprise Inc has partnered with PATH to develop a safe, effective, and low-cost third-generation pneumococcal conjugate vaccine (PCV) that will prevent invasive pneumococcal disease (IPD), pneumonia, and acute otitis media due to the remaining predominant serotypes causing disease in children, particularly those residing in Africa and other low- and middle-income regions of the world. The resulting candidate vaccine (IVT PCV-25) contains capsular polysaccharides from 25 pneumococcal serotypes: 1, 2, 3, 4, 5, 6B, 6C, 7F, 8, 9N, 9V, 10A, 12F, 14, 15A, 15B, 16F, 18C, 19A, 19F, 22F, 23F, 24F, 33F, and 35B.

The IVT PCV-25 vaccine was recently tested in a randomized, active-controlled, observer-blind, Phase 1 study (CVIA 096) to evaluate the safety, tolerability, and immunogenicity in adults (NCT05540028) at the Canadian Center for Vaccinology, Dalhousie University, IWK Health Centre Halifax, Nova Scotia, Canada. The single dose of IVT PCV-25 vaccine or the comparator PCV Prevnar 20™ was administered to 60 adults aged 18-40 years in a randomization ratio of 1:1. Analysis of the unblinded adult group-level serotype-specific IgG responses which indicated a lower geometric mean ratio in several of the serotype-specific IgG responses in participants who received IVT PCV-25 compared to those participants vaccinated with Prevnar 20™ and review of the Prevnar 20™ pediatric data presented to the American Committee on Immunization Practices (<https://www.cdc.gov/vaccines/acip/meetings/downloads/slides-2023-02/slides-02-22/Pneumococcal-04-Watson-508.pdf>; <https://www.cdc.gov/vaccines/acip/meetings/downloads/slides-2023-02/slides-02-22/Pneumococcal-05-Kobayashi-508.pdf>) led Inventprise, Inc (Sponsor) advised by its Scientific Review Committee to suspend the enrollment of the young child and infant cohorts originally planned in the Phase 1 trial. Inventprise, Inc. has reformulated IVT PCV-25 into three different formulations of antigen and adjuvant combinations to be tested in this new dose ranging Phase 2 trial in adults only.

The Data and Safety Monitoring Board (DSMB) reviewed the safety data after the single dose immunization in the 60-person adult cohort (NCT05540028) through day 29 and determined that the reactogenicity and safety were favorable and approved moving forward in age de-escalation prior to the Sponsor's decision to suspend the trial. No SAEs occurred, and Grade 3 AEs were determined to be unrelated to investigational product(s). The adult cohort [REDACTED] will continue safety follow-up through study end (day 169, estimated July 2023) for all 60 adult participants enrolled in the study, after which the study will be terminated.

This Phase 2 trial of IVT PCV-25 is designed to provide the necessary assurances of safety, reactogenicity, and immunogenicity of a single dose of three different dose-ranging formulations of IVT PCV-25 in order to proceed directly to infants for a dose-finding Phase 2 trial [REDACTED]

2 Hypothesis, Objectives and Endpoints

2.1 Study Hypotheses

IVT PCV-25 will have an acceptable tolerability and safety profile in adults. IVT PCV-25 will be immunogenic and will elicit seroresponses to the serotypes present in the candidate vaccine. All analyses in this study are considered descriptive and no statistical test of this hypothesis is planned.

2.2 Study Objectives

2.2.1 Primary Objective: Safety and Tolerability

To assess the reactogenicity, tolerability, and safety of IVT PCV-25 administered as a single-dose regimen to healthy pneumococcal vaccine-naïve young adults.

2.2.2 Secondary Objectives: Immunogenicity

To describe the immune responses elicited by a single dose of IVT PCV 25 against the 25 serotypes contained in IVT PCV-25 (1, 2, 3, 4, 5, 6B, 6C, 7F, 8, 9N, 9V, 10A, 12F, 14, 15A, 15B, 16F, 18C, 19A, 19F, 22F, 23F, 24F, 33F, 35B) as well as serotype 6A, alone and in comparison to the antibody responses against these serotypes induced by Prevnar 20TM in healthy adults

2.3 Study Endpoints and Estimands

2.3.1 Primary: Safety and Tolerability

Table 1: Primary Endpoints and Estimands

ENDPOINTS	ESTIMANDS
-----------	-----------

 1. Local reactions (redness, swelling, and pain at the injection site) 2. Systemic events (fever, headache, fatigue, muscle pain, joint pain, and rash) 3. Unsolicited Adverse events (AEs) 4. Serious adverse events (SAEs) 	
Population: Healthy pneumococcal vaccine-naïve adult participants receiving study vaccines
 
Population-level summary:
 
 1. Number and severity of solicited local reactions within 7 days after vaccination (redness, swelling, and pain at the injection site) by group 2. Number and severity of solicited systemic AEs within 7 days after vaccination by group 3. Number and severity of unsolicited AEs within 28 days after vaccination by group 4. Number of SAEs within 6 months after vaccination by group
---	---

2.3.2 Secondary: Immunogenicity

Table 2: Secondary Endpoints and Estimands

ENDPOINTS	ESTIMANDS

 1. Serotype-specific immunoglobulin G (IgG) antibody responses 2. Serotype-specific functional antibody responses measured by Opsonophagocytic Assay (OPA) 	
Population: Healthy pneumococcal vaccine-naïve adult participants receiving study vaccines, complying with the key protocol criteria, and providing evaluable sample at baseline and 28 days after vaccination
 
Population-level summary:
 
 1. Geometric mean concentrations (GMC) of serotype-specific IgG at each time point (Day 1 and Day 29) by group 2. Geometric mean fold rise (GMFR) in serotype-specific IgG GMCs from baseline to Day 29 after vaccination by group 3. Percentage of participants achieving a ≥ 4-fold IgG rise from baseline to Day 29 after vaccination by group 4. Ratio of GMCs between IVT PCV-25 and Prevnar 20 groups 28 days after vaccination 5. Ratio of IgG GMFR between IVT PCV-25 and Prevnar 20 groups 6. Geometric mean titers (GMTs) of serotype-specific OPA antibodies at each time point (Day 1 and Day 29) by group

	
 7. Geometric mean fold rise (GMFRs) in serotype-specific OPA GMTs from baseline to Day 29 after vaccination by group 8. Ratio of GMTs between IVT PCV-25 and Prevnar 20 groups 28 days after vaccination 9. Ratio of OPA GMFR between IVT PCV-25 and Prevnar 20 groups
--	--

3 Study Design

In this prospective, multicenter, randomized, active-controlled, observer-blind Phase 2 study, 220 adult (age 18-49 years) eligible participants will be randomized to four groups as shown below (Table 3). The four groups will be conducted concurrently and randomized in a 2:3:4:2 ratio.

Each adult will undergo a total of 4 clinic visits (V), including at least one screening visit (V0) not more than 28 days prior to Day 1 (V1), a vaccination visit on Day 1 (V1), follow-up clinic visits at 7 (+3) and 28 (+14) days post-vaccination (V2 and V3, respectively) as shown in Table 8 in Appendices. Re-screening is permissible if the window period exceeds 28 days. Daily local and systemic reactogenicity will be monitored during the 7 days after vaccination (Day 1 and following 6 days) by memory aid. Blood will be collected for hematological and biochemical laboratory tests at screening (V0) and Day 8 (V2). Blood will be collected at baseline (V1) and 28 days post-vaccination (V3) to assess serotype-specific IgG antibody and OPA functional antibody responses in all participants. There will be a final follow-up call on Day 169 (V4).

The study visit schedule is presented in Table 8 in the Appendices.

4 Statistical Considerations

4.1 Overview

This is a multicenter, randomized, active-controlled, observer-blind Phase 2 trial in 220 healthy adults (age 18-49 years) residing in Canada. Eligible participants will be randomized to four groups as shown below (Table 3) in a 2:3:4:2 ratio.

No formal statistical hypothesis tests between treatment groups are planned in this study. All analyses for safety and immunogenicity data will be descriptive. When appropriate, continuous data will be summarized using descriptive statistics such as number of subjects with non-missing values, mean, standard deviation (SD), median, minimum, and maximum. Categorical data will be presented using the percentage of subjects in each category. A two-sided 95% CI will be provided for estimates, as appropriate. Individual subject data will be provided in listings. All statistical analyses will be performed using SAS® software Version 9.4 or later. Subject-wise data listings will be provided.

4.2 Randomization

An interactive web response system (IWRS) will be used to randomize participants to the four study groups in a ratio of 2:3:4:2, as shown in shown in Table 3. A block randomization scheme will be employed to ensure that the randomization ratio is maintained among the treatment groups at each site.

Table 3: Randomization Scheme

Group	n		
Group D	40	Prevnam 20™ comparator	Prevnam 20

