#### 7.1 Sample Collection, Distribution, and Storage

Samples to evaluate vaccine safety in adults will be obtained and processed at each trial site and transported to each site's clinical laboratory for testing. Research specimens collected for the immunogenicity endpoints will be separated into aliquots by each site's processing laboratory as per the Lab Manual and stored at  $\leq -70^{\circ}\text{C}$  in their storage facilities before being shipped to the central immunology laboratories (see Section 7.3). Continuous temperature monitoring and backup generators will be in place to ensure proper sample storage.

Volumes of blood required for adults are shown in Table 10. These volumes are for the expected standard laboratory testing; retesting may require additional blood draws. Provision for additional blood draws (for the purposes of safety assessments) will be included in the ICF.

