## 11.2 Randomization Procedures

The enrolled participants will be randomized in a ratio of 2:3:4:2 to receive IVT PCV-25 [REDACTED] IVT PCV-25 [REDACTED] IVT PCV-25 [REDACTED] or Prevnar 20™, respectively with secure interactive response technology (IRT). An Interactive Web Response System (IWRS) will be the primary method of randomization, however a back-up randomization method will be available, if necessary. The study site(s) will be allocated blocks to maintain the randomization ratio(s) at each site. The randomization schedule will be prepared by the CRO statistician.

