4.6.6 Analysis of Secondary Objective

The analysis of immunogenicity will be performed on the PP population as the primary analysis and the full analysis population as a secondary analysis.

Immunogenicity data will be descriptively analyzed. Serotype-specific IgG antibody responses will be measured at baseline (V1), and 28 days after study vaccination (V3).

- GMC with two-sided 95% CIs
- GMFR from baseline with two-sided 95% CI
- Percentage of participants achieving a ≥ 4 -fold IgG rise from baseline to Day 29 after vaccination by group with two-sided Clopper-Pearson 95% CI

Serotype-specific functional antibody responses will be measured by OPA and summarized at baseline (V1) and 28 days after study vaccination (V3),

- GMTs with two-sided 95% CIs,
- GMFR from baseline with 95% CI

GMCs and GMTs will be calculated for each treatment group along with their two-sided 95% CI, by exponentiating the corresponding log-transformed mean and their two-sided 95% confidence limits.

The ratio of the GMC/GMT between IVT PCV-25 formulations [REDACTED] to Prevnar 20TM and corresponding two-sided 95% CI will be provided. The log-transformed antibody responses will be used to construct a mean difference between the treatment groups and the comparator vaccine, Prevnar 20TM and its two-sided 95% CI using the two-sample t-test method. The mean difference and corresponding 95% CI will be back-transformed to obtain the GMC/GMT ratio between the two groups and corresponding 95% CI.

An adjusted GMC/GMT ratio between the treatment groups will be also provided along with its two-sided 95% CI. The log-transformed antibody responses will be used to compute a mean difference between each of the IVT PCV-25 groups and the Prevnar 20 group, along with corresponding two-sided 95% CIs, using analysis of covariance (ANCOVA) with log-transformed baseline antibody responses as a covariate. Other variables, such as age and sex, will be evaluated for inclusion in the ANCOVA model as well, using stepwise selection method. The mean difference and its 95% CI will be exponentiated to obtain the adjusted GMC/GMT ratio between the two groups and corresponding 95% CI.

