GMFRs and corresponding two-sided 95% CIs will be computed for each treatment group. The mean difference in the log-transformed antibody responses between 28 days post vaccination and baseline and corresponding two-sided 95% CI will be calculated using the paired t-test method and then back-transformed to obtain GMFR and its 95% CI. The two-sample t-test method will be used to obtain the two-sided 95% CI of the ratio of GMFRs between the study groups. The distribution of concentrations/titers will be summarized using reverse cumulative distribution (RCD) curves at applicable time points. Forest plots will be created to visualize the IgG and OPA GMRs at 28 days post-vaccination. The distribution of antibody concentrations/titers at baseline and 28 days post-vaccination, as well as their fold-rises at 28 days post-vaccination, will be summarized using box plots.

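### Randomisation is blocked within site but no immunogenicity model names site; if responses differ by site, the ANCOVA intervals are somewhat wider than they need be

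*SAP*

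**What the plan says.** SAP 4.2 uses an IWRS to "randomize participants to the four study groups in a ratio of 2:3:4:2" and states that "A block randomization scheme will be employed to ensure that the randomization ratio is maintained among the treatment groups at each site". Protocol 11.2 says the same: "The study site(s) will be allocated blocks to maintain the randomization ratio(s) at each site". Neither document names another balancing factor.

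SAP 4.6.6 then sets out the between-group immunogenicity intervals:

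- Unadjusted GMC/GMT ratio: a log-scale mean difference and "its two-sided 95% CI using the two-sample t-test method".
- Adjusted GMC/GMT ratio: "using analysis of covariance (ANCOVA) with log-transformed baseline antibody responses as a covariate".
- Further covariates: "Other variables, such as age and sex, will be evaluated for inclusion in the ANCOVA model as well, using stepwise selection method".
- GMFR ratio: "The two-sample t-test method will be used to obtain the two-sided 95% CI of the ratio of GMFRs between the study groups".

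Protocol 11.5.6 matches, except that it does not specify stepwise selection. Site appears in none of these, and no reason is given. The SAP also does not say whether the ANCOVA is fitted once to all four groups or separately for each formulation against Prevnar 20.

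**The concern.** When randomisation is blocked within site, differences between sites largely cancel out of the treatment contrast. If the analysis leaves site out, those differences stay in the residual variance and the standard error is larger than the contrast warrants.

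Site differences are possible here. Sites recruit their own participants, and Protocol 7.1 has each site's laboratory process and store sera before shipment: "Research specimens collected for the immunogenicity endpoints will be separated into aliquots". The assays themselves are run centrally, so any site effect would come mainly from participants and sample handling.

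The stepwise clause adds a second difficulty. There are 26 serotypes (25 plus 6A) and two assays. If site is a candidate covariate, it could enter some models and not others, and the ratios shown together in the forest plots would come from different models.

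What is at stake is precision in the estimates the sponsor will use to judge whether responses suffice to plan an infant study. At the interim the comparator has about 18 evaluable participants after attrition.

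**Working it through.** **1. The plan's own figure.** Inputs from SAP 4.3: log10 SDs of 0.5 and 0.45, true ratio 0.75, 10% attrition (20/30/40 become 18/27/36). Formula: 10^(log10 0.75 ± t × SE), SE = √(s1²/n1 + s2²/n2), Welch degrees of freedom.

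- 18:18: SE = √(0.25/18 + 0.2025/18) = 0.159, giving (0.357, 1.575). Stated: (0.36, 1.58).
- 27:18: (0.385, 1.461). Stated: (0.38, 1.46).
- 36:18: SE = √(0.25/36 + 0.2025/18) = 0.135, giving (0.400, 1.407). Stated: (0.40, 1.41).

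All agree to within 0.01. The planned precision therefore has no site term.

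**2. Adding site, simple two-arm formula.** Let ρ be the between-site share of the log10 variance and S the number of sites. The documents give neither, so both are assumptions. With balanced sites, adding site multiplies the SE by √(1 − ρ) and costs S − 1 degrees of freedom. For a like-for-like comparison, the starting point is the pooled t. At 36:18 the pooled variance is (35 × 0.25 + 17 × 0.2025)/52 = 0.2345, SE = √(0.2345 × (1/36 + 1/18)) = 0.140, and the interval is (0.39, 1.43). With S = 5:

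| ρ | Change in log-scale width | Interval |
|---|---|---|
| 0 | +0.2% | (0.39, 1.43) |
| 0.02 | −0.8% | (0.40, 1.42) |
| 0.05 | −2.3% | (0.40, 1.41) |
| 0.10 | −4.9% | (0.41, 1.39) |

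Site pays for itself once ρ exceeds a break-even share. At 18:18 that share is 0.010 with 5 sites, 0.019 with 8 and 0.026 with 10. At 72:36 it is about 0.002 or less.

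**3. Simulated four-group ANCOVA, full data.** Assumptions: blocks of 11 (2 + 3 + 4 + 2), 20 blocks (220/11) over 5 or 8 sites, 10% attrition, baseline correlation 0.5, with ρ now the site share of residual variance.

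- No site effect: +0.1 to +0.3% in width.
- 5% share: about −2%.
- 10% share: about −4%.

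A hand check explains why this is slightly less than in step 2. With S equal sites, only about (S − 1)/S of the between-site variance reaches the residual when site is omitted. The width ratio is then about √[(1 − ρ)/(1 − ρ + ρ(S − 1)/S)]. For S = 5, ρ = 0.05 gives √(0.95/0.99) = 0.980, and ρ = 0.10 gives √(0.90/0.98) = 0.958.

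In participants, 2% and 4% narrower intervals correspond to 1/0.98² = 1.04 and 1/0.96² = 1.085, that is, about 4% and 8.5% more.

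Coverage without site was about 95% with no site effect and rose to about 97% at a 20% share. The error is on the conservative side.

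**4. Interim data.** The interim IgG set is whatever is available from roughly half or more of participants, so balance within site is not assured. Taking a random half as available (an assumption), adding site in the joint four-group ANCOVA gave:

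- No site effect: +1.3 to +2.4%.
- 5% share: −0.8% with 5 sites, +0.1% with 8.

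If each formulation is instead fitted only with Prevnar 20, the A-versus-D interval widens by about 5 to 9% with no site effect, and still by about 2.5 to 6% at a 5% share. If the available samples form complete blocks (10 blocks), the joint-model cost falls to +0.2 to +0.6%.

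**The case against.** A reader might infer that the planned intervals are definitely wider than the design allows. The documents do not support that. They report no between-site variance and no number of sites, and if sites do not differ, adding site widens the intervals slightly. Central assays, one country, and healthy vaccine-naïve adults aged 18 to 49 all argue against a large site effect. Differences already present at baseline are partly absorbed by the baseline covariate, and they drop out of fold rises if they persist to Day 29.

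A reader might also infer that site is excluded from the ANCOVA. It is not: the covariate list is open-ended, so site is unnamed rather than ruled out. That limits the claim, but it does not settle the matter, because selecting a blocking factor from the data, serotype by serotype, is a weak way to handle it.

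The interim objection stands in part. With an unbalanced half of the samples, site can cost more than it gains, especially in pairwise models. That is a reason for a joint model and a pooling rule.

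Finally, the endpoints are secondary and descriptive, with no tests and no numeric threshold for proceeding. Moving an interval from (0.39, 1.43) to (0.40, 1.41) changes no stated decision. That stands, and it keeps the point small.

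**Conclusion.** The point holds in conditional form. Site is the only factor the randomisation is said to balance, and no immunogenicity model names it. If responses differ by site beyond a small break-even share, the ANCOVA intervals are conservative and wider than needed.

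On full data the gain from adding site is about 2 to 4% of interval width, assuming 5 to 8 sites and a 5 to 10% site share of residual variance. The cost is about 0.1 to 0.3% if there is no site effect. The omission itself is certain from the text; the size of the gain rests on those assumptions. It would be wrong to read this as a validity problem, since estimates stay unbiased and coverage is nominal or slightly above. It is a low-priority improvement that also closes a gap left by the stepwise clause.

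**What to change.** In SAP 4.6.6, specify one joint four-group ANCOVA per serotype and assay, with log baseline and site as fixed terms held outside the stepwise selection. Apply it to the OPA data at the second analysis, and to the complete IgG and OPA data at the final analysis.

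For the interim IgG analysis, use the same joint model with small sites pooled by a rule fixed before the first unblinding. One option is to pool sites with fewer than 11 participants, one full block under the assumed block size. Pooling should reduce the interim cost, but that was not tested here. The unadjusted t-based GMC/GMT and GMFR ratios can stay as they are. If the sponsor prefers to leave site out, the SAP should say so and give the reason.

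The cost is a short SAP edit and S − 1 degrees of freedom. Without pooling, interim intervals would be about 1 to 2.5% wider if sites do not differ and a random half of samples is available.
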